Study Title Power-Up: An Effectiveness Trial of the Diabetes Prevention Program
NCT Number NCT04104243
IRB Protocol ID 2019-10343
Protocol Approval Date 9/19/2024

This proposal responds to PA-16-428, “Health Promotion Among Racial and Ethnic Minority Males,” with *Power-Up for Health*, an effectiveness trial of an adapted National Diabetes Prevention Program (NDPP) tailored to engage men with prediabetes and offered through primary care settings that serve disadvantaged urban communities. The rising epidemic of type 2 diabetes is a major cause of disability and death that disproportionately affects men. The burden of diabetes for men is further compounded by well-documented racial/ethnic disparities in diabetes risk, prevalence, control and health outcomes. Despite this disproportionate impact, effective diabetes prevention programs largely fail to reach and engage men. Gender disparities in NDPP participation are typically stark, with men averaging 20% of participants, although men who do participate achieve equivalent or better weight loss, compared to women. It remains mostly unknown to what extent failure to engage men in NDPP represents limited reach (i.e., proportion of the eligible population who participate) of standard recruitment efforts, typically based on physician referral, versus poor engagement (i.e., participation in and exposure to the intervention) and retention. Results from our 2-year pilot study (R18 DK102080) show that *Power-Up* can be successfully implemented and achieve similar weight loss, as compared to NDPP, but rigorous evaluation is needed.

The proposed study builds on this successful NIDDK-funded pilot work to address the clear need for a men-tailored approach to diabetes prevention. *Power-Up* is an intervention that is: a) tailored to the needs and preferences of racial/ethnic minority men; b) delivered by men coaches in men-only groups; and c) uses adapted content that highlights issues relevant to men and messaging designed to be acceptable and engaging to men. Based on the pilot results, we propose to conduct a rigorous effectiveness evaluation using a pragmatic RCT design within diverse healthcare settings already implementing standard mixed-gender NDPP. The goals of this study are to: 1) test the effect of *Power-Up* on weight loss; 2) evaluate engagement of men in *Power-Up*; and 3) examine the reach, broader effectiveness, implementation, and costs of *Power-Up* to inform future dissemination efforts and plans for sustainability.

The proposed study will leverage existing collaborations with co-investigators testing best practices for recruitment, implementation and evaluation of NDPP in a bureau of the New York City Department of Health and Mental Hygiene. Through this partnership we will recruit 300 men from across a spectrum of primary care centers - from a major urban academic medical center to small- and medium-sized primary care practices throughout New York City serving disadvantaged communities. Electronic Health Record data will facilitate outreach to the population of eligible men, based on NDPP criteria, rather than relying on physician referral, and will establish a valid denominator for the total population of eligible men, allowing for a rigorous assessment of the reach of our recruitment approach and an evaluation of the representativeness of our sample. Indicators of effectiveness, adoption, implementation and cost will be analyzed, guided by the RE-AIM framework.

Aim 1. Assess the effect of *Power-Up* vs. NDPP on weight loss among racial/ethnic minority men at risk for diabetes.

Hypothesis 1 (Primary Outcome): Men randomized to *Power-Up* will achieve significantly greater weight loss at 16-weeks and 1-year than men in the standard care group referred to mixed-gender NDPP classes.

Aim 2. Compare engagement of racial/ethnic minority men at risk for diabetes in *Power-Up* vs. NDPP.

Hypothesis 2 (Secondary Outcome): Men randomized to *Power-Up* will have significantly greater engagement rates (i.e., attend at least 4 sessions) and retention rates (i.e., attend 9 or more sessions) than men randomized to standard care and referred to mixed-gender NDPP classes.

Aim 3. Evaluate the Reach, Effectiveness, Adoption, Implementation, and Costs of *Power-Up*.

(Exploratory outcomes) Use the RE-AIM framework to evaluate: 1) the reach of our recruitment methods and the representativeness of men who enroll in the study, are successfully engaged, and who are successfully retained in *Power-Up* vs. standard NDPP, relative to the eligible population; 2) the broader effectiveness of *Power-Up* based on patient-reported outcomes [e.g., self-reported health, health behaviors, psychosocial factors] and routinely measured clinical data [e.g., change in blood pressure, change in HbA1c]; 3) adoption of *Power-Up* at the practice level; and 4) the fidelity and consistency of implementation and total program costs of *Power-Up*.

Recruitment and Retention Plan

RECRUITMENT STRATEGY. We will select sites based on availability of virtual NDPP classes. As the sessions are taking place virtually the site does not need to be near the participant. Having the Prevention Outreach Specialist at PCIP/DOH trained as a Master Trainer will ensure we are able to support NDPP efforts at PCIP/DOH small and medium sized practices over time, by training additional NDPP coaches if necessary. We expect a high rate of participation among approached practices, based on our experience in *NYC Care Calls* where 11 out of 12 approached practices agreed to participate. To offset some of the burden of participating in a study such as this for small and medium sized practices that may not have the resources and larger institutional support for research, we have budgeted \$1000 stipends for each participating practice in the PCIP/DOH network. We expect to engage approximately 20-30 practices across the two partnering healthcare systems to meet our recruitment goals. We will also contact eligible participants within Montefiore Medical Group.

After securing an agreement from a given practice, we will use EHR search capabilities to generate lists of men who: 1) meet all of the following NDPP criteria based on EHR values— at least 18 years old, most recent BMI ≥ 25 (within last 6 mos), most recent HbA1c: 5.7%–6.4% (within last 12 months); and 2) received care at a NYC-based PCIP health care clinic in the past 12 months. A physician from the practice will have the opportunity to review these lists and exclude any patient they deem inappropriate for participation based on serious mental illness, dementia or other cognitive problems, or physical disability that would prevent attendance and participation in the intervention sessions or telephone surveys. Reasons for exclusion will be recorded and coded systematically. Participants will be contacted via phone without sending an opt-out letter. PCIP/DOH and Montefiore Medical Group (MMG) participant outreach does not mail letters to participants in standard care therefore they will be contacted as they are contacted normally.

To be fully eligible, men must: 1) have no plans to change their primary care provider or move from their current address in the next year; 2) must agree that they are able and willing to attend virtual, group-based diabetes prevention classes; 3) must complete the baseline survey assessment and be willing to complete follow-up study surveys and procedures for collecting study weights; and 4) must provide informed consent by telephone, including consent for study participation, data collection, and random assignment to *Power-Up* or standard care NDPP. These methods for recruitment, eligibility screening, and oral consent have been previously approved by the NYC DOHMH and the Albert Einstein College of Medicine IRBs and are based on our successful recruitment for the NYC Care Calls Study (R18 DK 09742), conducted in partnership with PCIP.

Since there are likely to be 30,000-40,000 men patients across all of the PCIP/DOH and MMG practices who meet the eligibility criteria, we will be unable to call and screen all at once. Instead, we will target a small number of particular practices at a time, closing recruitment at these sites and moving on to other practices as we exhaust the full population of potentially eligible men at each site. We will also limit contact to those men who have had their weight measured within the last 6 months to limit the possibility that men will no longer be eligible for the programs based on weight and to increase the precision of our estimates for missing study-weights in the case of missing data or loss to follow-up. Our recruitment procedures represent a departure from current NDPP recruitment practices at PCIP/DOH and MMG practices, which rely on physicians to identify eligible patients and refer them to the NDPP. We expect that this active outreach approach will allow us to reach our recruitment goal of 300 enrolled participants given the large population of potentially eligible patients available through our health system partner. Given that we will not reach all practices in these networks, we will also be able to compare the reach and representativeness of our male sample across both arms of the trial, using EHR-based outreach, to that achieved by non-participating practices within our healthcare system partners' networks that continue to rely on physician referral for recruitment into NDPP.

RETENTION STRATEGIES. Our retention strategies are informed by our experience with the pilot and prior health behavior change and lifestyle intervention studies conducted by our team involving longitudinal follow-up of participants over 12 months or more. Based on this experience, we will provide monetary incentives for completion of telephone-administered surveys and for presenting for the collection of weights at the designated intervention session (e.g., 16 weeks and 12 months), which will be mailed to participants via the use of Clincards. We will also send reminders via text message, email, and/or mail for all first session, 16-week and 12 month weigh-ins, across both arms of the study. In addition, we will send cards in the mail to keep rapport by acknowledging birthdays and holidays and updating participants of the study. Participants will be supplied with scales to track their weight remotely.

Development of study branding with a graphic designer to be used in all study communications and materials and sending periodic mailings to participants to remind them of upcoming appointments for surveys or weight-collection will also be helpful in fostering a sense of ongoing participation and helping participants keep their appointments. Bonding of participants within groups is one of the most important retention strategies promoted by the coaches. For example, buddy activities and raffle ticket giveaways during the class sessions have improved group cohesion and class retention in prior DPP efforts. Well-trained coaches who are cognizant of retention issues are likely the most effective strategy to reduce attrition. Coaches use texts and email in addition to phone calls to remind participants of upcoming sessions, address missed sessions and troubleshoot issues that come up regarding attendance. For example, when a participant misses a session, the coach will typically text and call the participant to make up the session via telephone and identify barriers to getting to session. Session scheduled times conflicting with work schedules and family commitments are the most common barriers identified. Thus, we have planned to hold sessions mostly in the evenings, with weekend sessions also available. Information from our baseline survey can also be used to help inform common reasons why a participant may miss sessions (e.g., childcare or complex work schedule). Participants will be contacted via text (with their permission) reminding them to complete study questionnaires, weigh-in prior to sessions, fill out their physical activity logs, and the link for joining the sessions.

PHS HUMAN SUBJECTS AND CLINICAL TRIALS STUDY

[figure not shown]
TIMELINE

We have planned our study to ensure sufficient time to recruit and follow-up our 300 participants before a 6-month period at the end of the study that will be concentrated on data analysis, writing-up of results, and dissemination. To achieve this goal, we will begin recruitment and implementation of the assessment and intervention procedures of the study at month 6 of the first year of funding. The first 6 months of the first year will be focused on hiring of staff, study-start-up, ordering of materials, setting-up databases for study variables, finalizing data extraction protocols, finalizing qualitative interviewing questions and procedures, and, finalizing procedures and intervention content in consultation with our expert Advisory Board. We have sufficient time to meet our study milestones and recruitment goals and plan time the cycles of intervention to ensure successful progress. The study will last 60 months, with start-up activities taking place in months 1-6. Intervention Cycles will run simultaneously between the 2 intervention settings over a 3-year period of the award. We will recruit 300, run 8 intervention cycles of approximately 40 men randomized 1:1 to each arm in months 13-54. Follow-up 16-week and 12-month assessments will be completed in months 24-54. Data analysis and dissemination activities will take place in months 55-60. Our budget allows us to hire 8 coaches in year 1 and up to another 8 coaches in year 3, ensuring our ability to run a sufficient number of groups.

Study Activity Timeline

Study Activity	Year 1		Year 2		Year 3		Year 4		Year 5	
Meetings with Advisory Board										x
Train coaches in implementation and data collection			x		x					
Recruitment data abstraction, mailings & outreach			x	x	x	x	x			
Baseline weight assessment and surveys			x	x	x	x	x			
Implement Power-Up sessions			x	x	x	x	x	x	x	
Observe Power-Up and DPP sessions for fidelity				x	x	x	x	x	x	
Practice Exit Interviews				x	x	x	x	x	x	
Follow-up weights and surveys (16 wks and 12 mos)				x	x	x	x	x	x	
Participant focus groups and individual interviews				x	x	x	x	x	x	
Lifestyle coach surveys				x	x	x	x	x	x	
Lifestyle coach interviews				x	x	x	x	x	x	
Analyses, publications, and reports for dissemination										x

Intervention Cycles Timeline

Each cycle consists of a 16-week core phase to be completed within 6-months () and six-month post-core maintenance phase of 6 sessions (.). The duration of each cycle is 10-12 months. Concurrent with each Power-Up Cycle, a similar number of NDPP sessions will be available for men assigned to the standard care, mixed-gender NDPP condition.

Inclusion Enrollment Report 1

Using an Existing Dataset or Resource* : ☐ Yes ☒ No

Enrollment Location Type* : ☒ Domestic ☐ Foreign

Enrollment Country(ies): USA: UNITED STATES

Enrollment Location(s): Domestic; primary care clinics in NYC

Comments: Entries reflect totals recruited across Montefiore and PCIP/ NYC-DOHMH sites

Planned

Racial Categories	Ethnic Categories				Total
	Not Hispanic or Latino		Hispanic or Latino		
	Female	Male	Female	Male	
American Indian/ Alaska Native	0	3	0	3	6
Asian	0	6	0	5	11
Native Hawaiian or Other Pacific Islander	0	1	0	0	1
Black or African American	0	71	0	62	133
White	0	70	0	63	133
More than One Race	0	5	0	11	16
Total	0	156	0	144	300

Cumulative (Actual)

Racial Categories	Ethnic Categories									Total
	Not Hispanic or Latino			Hispanic or Latino			Unknown/Not Reported Ethnicity			
	Female	Male	Unknown/ Not Reported	Female	Male	Unknown/ Not Reported	Female	Male	Unknown/ Not Reported	
American Indian/ Alaska Native	0	0	0	0	0	0	0	0	0	0
Asian	0	0	0	0	0	0	0	0	0	0
Native Hawaiian or Other Pacific Islander	0	0	0	0	0	0	0	0	0	0
Black or African American	0	0	0	0	0	0	0	0	0	0
White	0	0	0	0	0	0	0	0	0	0
More than One Race	0	0	0	0	0	0	0	0	0	0
Unknown or Not Reported	0	0	0	0	0	0	0	0	0	0
Total	0	0	0	0	0	0	0	0	0	0

PROTECTION OF HUMANSUBJECTS

1. Risks to Human Subjects

1a. Human Subjects Involvement, Characteristics, and Design. We will evaluate our Aims within a healthcare system that is implementing the NDPP as a standard of care via a practical two-arm randomized controlled trial (RCT), where eligible men are randomly assigned to receive either *Power-Up* or standard, mixed-gender NDPP.

The study will be carried out by Albert Einstein College of Medicine (AECOM) and PCIP/NYC-DOHMH-based study staff. A co-investigator from PCIP/DOHMH, [name] is participating in this proposal and will have responsibility for engaging primary care practices based on their knowledge of the practice population and preliminary searches of electronic databases. Practices that have well established procedures for referring to the NDPP and that have access to robust NDPP programming in English and Spanish will be prioritized to ensure equipoise of the RCT arms with respect to exposure to intervention. Practices serving large numbers of Black, Hispanic, and/or Spanish speaking patients will also be prioritized.

Study Sites	Site Investigators
Albert Einstein College of Medicine	
[name], MPH (PI)
 
[name] (PI)
 
[name], RN, CDE (Co-I)
 
[name] (Co-I)

Primary Care Information Project/New York City Department of Health and Mental Hygiene	[name] (Co-I)

Participant eligibility will be ascertained by PCIP and AECOM staff. Based on electronic health record (EHR) searches, we will generate lists of men who: 1) meet all of the NDPP criteria – at least 18 years old, most recent BMI ≥ 25 (within last 6mos), most recent HbA1c: 5.7%-6.4% (within last year); and 2) have valid address and telephone contact information. Participants will be contacted via telephone without receiving an opt-out letter. To be fully eligible, men must: 1) have no plans to change their health system or move from the NYC area in the next year; 2) be physically able and willing to attend virtual, group-based sessions; 3) complete baseline phone surveys and be willing to complete follow-up surveys and procedures for collecting study weights (See C.8.a of Research Strategy); and 4) provide informed consent by telephone. These methods for recruitment, eligibility screening, and oral consent have been previously approved by the AECOM IRB and are based on our successful recruitment for *NYC Care Calls* (See C.2.e of Research Strategy).

1b. Study Procedures, Materials and Potential Risks.

Study procedures will primarily take place in our study offices at AECOM and PCIP/NYC-DOHMH and at local sites of participating practices from the PCIP and MMG networks. Additional procedures for weight collection, when participants do not attend intervention sessions where weights are primarily measured, may take place at additional sites. Recruitment, eligibility screening, and enrollment procedures will be conducted by research assistants/prevention outreach specialists located at our AECOM and PCIP/NYC-DOH offices. Potentially eligible men will be: via telephone follow-up; informed of their risk for diabetes and the availability and efficacy of the DPP; evaluated for eligibility; asked to provide oral informed consent by phone; and then randomized to one of the two conditions. Random assignment will be conducted using envelopes with the randomization condition inside. The research coordinator will have access to the envelopes. Study coordinators will contact the research coordinator who will tell the SC which condition the participant will be receiving. Randomization will occur at AECOM for all participants. Random assignment, and final enrollment into the study will occur after telephone screening, and completion of baseline surveys. With leadership from [name] (Co-I), all

coach training for *Power-Up* intervention delivery will occur in AECOM or PCIP/NYC-DOHMH meeting space. NDPP training for coaches will occur through established programs.

Materials for the study include digitally measured weight (via GSM connected BodyTrace scales), intervention session attendance records, EHR-16 clinical data, survey responses, digital recordings of individual interviews, and focus groups, and fidelity ratings from coaches, as well by the PIs, based on observation of sessions. These materials will be collected using internet connected scales, by telephone or by remote search of EHR systems by staff based at our study offices. *Power-Up* sessions (16 core sessions delivered over 6 months and 8-10 additional maintenance sessions delivered over the subsequent 6 months for a total of 24 sessions over one year) will also be conducted virtually. Participants will be given the sessions digitally or a paper copy will be mailed out to them upon request. All participants will receive activity, food and weight logs by mail. Participants will also receive a handout on applications and action plans. Surveys of validated self-report questionnaires for psychosocial and behavioral variables will be conducted by telephone by study staff at our AECOM and study offices. These surveys will occur at baseline/enrollment (immediately prior to randomization), at approximately 16-weeks (goal to conduct this survey within a window of +/- 1 month of the 16-week intervention session), and 12-months (goal of +/- 1 month of the 12-month final maintenance session). Surveys may also be conducted by phone, where necessary (e.g., meeting a participant who missed a session to collect weight and administering the survey of self-reports in person, via the same procedure of reading the questions and response scales to the participant, as implemented during telephone administration). Study staff and trained coaches will collect and manage all primary data. Study staff will review coach-collected data on weights, heights, and attendance, as well as coach-completed fidelity checklists, for quality assurance, providing immediate feedback through prompt communication with coaches, by phone, text or in-person to address any quality issues. Protocols for qualitative data collection will be finalized with guidance from [name] (Consultant) and recordings and transcripts will be securely stored at our study offices. Daily activities of staff will be managed by an onsite project manager at each study office site. All staff will be trained, overseen and advised by Drs. [name] and [name] (PIs). The control arm weight and attendance data collection of men assigned to standard care NDPP will be supervised by [name] and for PCIP by [name] in collaboration with [name] (PCIP, co-I).

The primary outcome measure will be percent change in weight at the end of the Core (16 weekly) sessions and at the end of 12 months. We will examine several process and moderating variables, based on a telephone survey of self-report measures validated for English and Spanish language and in-person and telephonic administration, as well as EHR-extracted clinical variables, such as A1c, blood pressure, lipids, etc. 6 months after the delivery of the final session weights will also be EHR-extracted from clinical visits during the 1-year trial period, the 6 month wait is to allow for the updating of EHR data. Extracting these weights will help us capture weights for those who never attended sessions. Coaches will record , weight (using wireless internet connected scales), session attendance logs via study- ID coded and de-identified data entry. They will also complete fidelity checklists. Both of these data entry protocols will be supervised for quality control by study staff. Staff will also track and keep records of all study- related costs. These records will be reviewed periodically by the project managers of each site and by [name] (Co-I). Through coach surveys, coach interviews and participant individual interviews and focus groups, we will examine perceptions of *Power-Up*, fidelity to the model, barriers and facilitators to implementation and engagement, and recommendations for improvement. Participant identifying information will only be known to the primary study staff. Identifying information will be stored separately from study data in locked file cabinets in our study offices. Data will not be shared between study staff of participating health care systems and de-identified data for *Power-Up* participants will be shared with the *Power-Up* data analyst ([name], Co-I) for analysis.

Potential risks of participation are minimal and include the possibility that some participants may feel uncomfortable answering questions, or talking about their weight, food habits, physical activity, and factors that affect behavior. The intervention does not convey more than minimal risk and there is no reason to suspect that any serious adverse events will be attributable to it. All participants will be strongly encouraged to speak to their health care provider about safe and appropriate levels of exercise, as they would for any change in

physical activity. The NDPP guidelines recommend increasing physical activity at a moderate level, such as brisk walking, but participants will choose their own activity outside of the Core and post-Core learning sessions.

Expression of intent to harm self and/or others. The study will not assess intent to harm self or others, however, though this is a low risk, subjects may express thoughts of harm to self and/or others while completing study questionnaires, especially as it relates to managing their pre-diabetes. Staff and coaches will be trained on how to appropriately respond to expression of intent to harm self or others, and will maintain a Manual of Procedures (MOP), which includes state law requirements and local emergency phone numbers. Healthcare providers can also be alerted about concerns regarding risk, with the participant's consent.

Other Risks. Taking part in this research study may involve providing information that participants consider confidential or private, including thoughts of harm to self and/or others. Coaches and study staff will be trained in emergency procedures for adverse health events that may occur by chance when they are interacting with participants. They will not provide any intervention themselves but will be trained to identify emergency situations (e.g., cardiac arrest) and in procedures to access emergency care (e.g., calling 911). In addition, there is a slight risk of a breach of confidentiality. Subject will be informed of confidentiality limitations in the informed consent. As described in detail below, every effort will be made to keep participant names and contact information secure; only research staff will have access to linked contact information and study data. Identifiers will be excluded from any participant data analyzed by the AECOM-based data analysts.

Alternative Treatments and Procedures. The alternative is for potential subject to not participate in the study. If potential participants decline to enroll in the study but express interest in accessing NDPP, we will inform them of the procedures to do so. All potential participants will be receiving care from sites that provide access to the NDPP.

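### Follow-up weights, and the payment for them, are tied to session attendance, which the trial expects to differ by arm, although the connected scales could supply a dated weight regardless of attendance

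*Protocol*

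**What the plan says.** Under Retention Strategies, the protocol offers money for completing telephone surveys and "for presenting for the collection of weights at the designated intervention session" at 16 weeks and 12 months. The same paragraph promises weigh-in reminders in both arms and states: "Participants will be supplied with scales to track their weight remotely".

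Section 1b (Study Procedures, Materials and Potential Risks) describes the sources of weight:
- Additional weight collection, "when participants do not attend intervention sessions where weights are primarily measured, may take place at additional sites".
- The study materials include "digitally measured weight (via GSM connected BodyTrace scales".
- Coaches record "weight (using wireless internet connected scales), session attendance logs".
- After the final session, "weights will also be EHR-extracted from clinical visits during the 1-year trial period". The stated reason is: "Extracting these weights will help us capture weights for those who never attended sessions".

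Section 1b also names percent weight change at the end of the core sessions and at 12 months as the primary outcome. Hypothesis 2, under Aim 2, states that men randomised to Power-Up "will have significantly greater engagement rates (i.e., attend at least 4 sessions) and retention rates (i.e., attend 9 or more sessions" than men referred to standard classes.

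**The concern.** Attendance happens after randomisation, and the trial itself predicts that it will differ by arm. If a weight is collected and paid for through attendance, then whether a man has a primary-outcome weight, when it was taken and on what kind of scale may all depend on attendance, and through it on arm. The comparison of percent weight change could then be affected by how weights were obtained as well as by how much weight was lost.

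The protocol recognises this kind of hazard elsewhere. Section 2a (Informed Consent) rejects consent at the first session, partly because restricting the sample to first-session attenders would harm representativeness and internal validity. Weights tied to sessions can bring a similar selection back when the outcome is measured. The dependence also looks avoidable, since classes are virtual and the scales transmit.

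**Working it through.** The protocol gives no attendance rate, effect size, standard deviation or dropout rate, so there is no stated figure to reproduce. The check has two parts.

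**1. Passages side by side**
- *Payment:* Retention Strategies attaches it to presenting at the designated session. Nothing attaches it to a transmitted reading.
- *Place and recorder:* section 1b makes sessions the main place of measurement and has coaches enter weight together with attendance.
- *Catch-up:* section 1b allows weighing elsewhere for men who miss sessions. It and Adverse Event Monitoring mention meeting men in person to collect missing weights. The wording is permissive in one place (may) and describes such meetings as occasional in the other.
- *EHR weights:* these come from clinic visits during the trial year, with no window given. The surveys do have one, of one month either side.
- *Scales:* participants receive them for remote use, and the study device is GSM-connected. No sentence sets a dated weigh-in at 16 weeks and 12 months that stands apart from attendance.
- *Monitoring:* under Recruitment Monitoring, men without outcome measures are analysed on what is available and are not counted as drop-outs. The 70% retention trigger uses that definition and so would not reveal a gap in weights between arms.

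**2. Illustration (every rate below is assumed)**

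*Missingness.* Let p be the share attending the weigh-in session, c the share of non-attenders who are weighed anyway, and a and n the mean percent change in attenders and non-attenders.

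Observed arm mean = [p·a + (1−p)·c·n] / [p + (1−p)·c]

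Take a = −4, n = −1, p = 0.50 in NDPP and p = 0.60 to 0.70 in Power-Up.
- True difference at p = 0.60: (0.60 − 0.50) × (−4 + 1) = −0.30. At p = 0.70: 0.20 × (−3) = −0.60.
- c = 0: both arms show −4, so the observed difference is 0.00 and the bias is +0.30 to +0.60. The missingness gap is 10 to 20 points.
- c = 0.5: NDPP shows (−2.00 − 0.25)/0.75 = −3.00. Power-Up shows (−2.40 − 0.20)/0.80 = −3.25 at p = 0.60, and (−2.80 − 0.15)/0.85 = −3.47 at p = 0.70. The differences are −0.25 and −0.47, so the bias is +0.05 to +0.13. The missingness gap is 5 to 10 points.
- c = 1: the bias is 0.

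Here missingness masks a real benefit of Power-Up.

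*Source.* Suppose that clinic weights read 0.5% to 1.5% of body weight above scale weights, that baseline is a scale weight, and that the share of follow-up weights from the EHR is 10 to 20 points higher in NDPP.

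Spurious difference ≈ offset × gap in share: 0.5 × 0.10 = 0.05 to 1.5 × 0.20 = 0.30 points, in favour of Power-Up.

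The two effects run in opposite directions, and their net sign is unknown.

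**The case against.** The strongest reply is that the contrast between a session weight and a home-scale weight is partly unreal. Classes are virtual, men are texted to weigh in before sessions, and coaches work from connected scales, so a session weight may already be a home reading. A reader might infer that a reading sent by a man who skipped the session is thrown away. No passage says so. What remains is that no passage makes such a reading the outcome, or pays for it.

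Other parts of the reply also stand:
- Catch-up weighing and reminders in both arms are real mitigations. They reduce the dependence, but catch-up is optional and is itself triggered by non-attendance or a missing weight.
- EHR weights are described as an additional source that helps with men who never attended, a narrower group than men who missed one weigh-in. The protocol does not say that a clinic weight of any date becomes the endpoint value.
- A constant percentage offset cancels for a man whose baseline and follow-up weights both come from the EHR.
- Hypothesis 2 concerns attending at least 4 and at least 9 sessions, not presence at the two weigh-in sessions. A gap there is plausible but not stated.
- That every man has a transmitting scale is read from two sentences together. Neither restricts it by arm, and neither confirms it for each arm.

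Source ranking and modelling can be left to a statistical analysis plan, which was not available here. What is collected and paid for cannot: an analysis can model missing weights but cannot recover readings that were never prompted.

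**Conclusion.** The point holds as a design improvement. As written, collection of the primary weight and payment for it depend on attendance, which the trial expects to differ by arm. Availability, timing and source of the weight may therefore differ by arm, and the stated mitigations only partly prevent this.

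A reader might go further and conclude that the design gives Power-Up a spurious advantage, or that source and missingness are certain to be confounded with arm. The document supports neither. Source differences could favour Power-Up, while selective missingness could hide a true benefit. The figures of 0.05 to 0.30 points for source and 0.05 to 0.60 points for missingness (c from 0.5 down to 0) rest wholly on assumed attendance, catch-up, weight change and offset. They show the kind of error that is possible and are not an estimate of it. The case for changing the text is that the dependence is avoidable at low cost, and that a bias of unknown direction cannot be argued away afterwards.

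**What to change.** Amend Retention Strategies and the weight-collection text in section 1b as follows:
- Name the scale-transmitted reading nearest the 16-week and 12-month target dates as the primary weight for every randomised man in both arms, whether or not he attends. State a window, for example the one month either side already used for surveys. The survey window is counted from the session, so define the weight target date so that it exists for men who do not attend.
- Pay the weight incentive for that reading instead of for presenting at a session.
- State that scales are supplied in both arms.
- Keep EHR weights within the same windows, as a flagged secondary source.

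The cost is wording, and no new equipment if the scales already go to both arms. The downside is that home readings are unobserved, so a rule for checking implausible readings is needed.
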